Glucose care gap	4.1) diagnosed diabetes; and 4.2) A1c above goal	4.1) ICD-10 codes E10, E11 at 1 inpatient or 2 outpatient encounters, or on the problem list, in the previous 2 years; and 4.2) most recent A1c>=7 on or before index date
Nephrology care gap	5.1) Stage 3b or 4 CKD; and	5.1a) most recent eGFR15-<30 cc/min/1.72m ² , or

	5.2) nephrology referral needed	5.1b) eGFR30-<45 cc/min/1.72m ² and UMACR >=30 mg/g; and 5.2) no completed nephrology visit in prior year
--	---------------------------------	---

The index visit is defined as the first visit at any randomized clinic during the accrual period at which the patient met these CKD-CDS intervention eligibility criteria and none of the exclusion criteria. The patient accrual period (for index visits) was 11 months, followed by a 18-month observation period, so that patients will have 18 to 29 months of post-index follow up (estimated median, 24 months).

Each patient was assigned to the clinic where their index visit took place and by extension to the randomized treatment group of that clinic. Patients with index visits at clinics randomized to the CKD-CDS intervention (or usual care) group were considered CKD-CDS intervention (or usual care) patients. A patient could have post-index visits, that may or may not be intervention eligible, at clinics randomized to the other treatment group. Following intent to treat principles, the patient's treatment group assignment will not change as a result of the clinic treatment group assignment or patient intervention eligibility at the post-index visits. Additionally, the index visit marks the beginning of each patient's 18-month observation period.

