option, no further action is needed at that day's visit. The decision support provided to the PCP is very specific and, if pharmacotherapy is indicated, decision support specifies either initiation or titration of specific drugs based on the drugs/doses the patient is currently taking, distance from goal, and other clinical considerations outlined above. The patient version of the CKD-CDS uses symbols to provide easy patient recognition of priority clinical areas and then suggests potential treatment options they can discuss with their provider. Presenting key CKD care recommendations when indicated (all of which are evidence based and capable of improving CKD care) allows the patient freedom to select his or her preferred treatment option from among several evidence-based potentially beneficial treatment options. Because patient preference for health-related actions varies across specific actions, offering several options improves the chance that a given patient may be interested in addressing at least 1 of the evidence-based options presented. Moreover, patient engagement is a key predictor of subsequent adherence and success of treatment, as we have previously shown in this patient population.⁶⁵⁻⁷⁰ It is important to realize that the printed page the patient receives *is designed to direct discussion to a set of prioritized evidence-based treatment options with likely benefit to that patient.

Step 4. Take action based on the decisions made: After discussing with the patient, the provider can then go ahead and order the recommendations suggested by the CDS such as labs, medication, e-consults or referrals to nephrology or other specialists. All actions taken are governed by the provider's clinical judgement and the patient's preferences, not by the CKD-CDS.

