8 STUDY ASSESSMENTS AND PROCEDURES

8.1 EFFICACY ASSESSMENTS

The data used to evaluate the effectiveness of CKD-CDS system on reducing 5 CKD care gaps will derive from the CKD-CDS tool itself (e.g., care gaps present at index visit) or the electronic health record (e.g., CKD diagnosis, ACEI / ARB orders). There are no scheduled assessment visits from accrued patients. Rather, data elements that document study eligibility and care gaps at the index visit, and outcome events that occur in the 18 months following the index visit, will be recorded in these electronic resources as care is delivered to patients, with the timing of care delivery driven by clinician and patient judgment. This clinic-based pragmatic trial will not direct the timing, manner or amount of care delivered to any accrued patient according to a pre-defined schedule.

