H3: Blood pressure control	post-index BP at goal	in 18 months post-index, average of up to two most recent SBP<130; and average up to two most recent DBP<80
H4: Glucose control	post-index A1c at goal	most recent A1c<7% in 1 to 18 months post-index
H5: Nephrology referral	nephrology referral	referral to or completed visit with nephrologist, on index date through 18 months post-index

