9.4 STATISTICAL ANALYSES

9.4.1 GENERAL APPROACH

All 5 hypotheses quantify the extent to which the CKD-CDS intervention relative to UC reduces deficits in measures of CKD care. Each will be defined as a single outcome based on data accrued in the 18 months after each patient's index visit. For all 5 measures, it is expected that the CKD-CDS intervention will positively impact the quality of care delivered to eligible patients with CKD.

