9.4.2 ANALYSIS OF THE PRIMARY EFFICACY ENDPOINT(S)

9.4.2.1. Analysis plan. All hypotheses will be tested using random coefficients models in which each binary post-index outcome (e.g., recognition in 18m) will be predicted via a link function from a fixed clinic-randomized treatment group predictor, Y_{10} ; fixed clinic predictors for characteristics balanced at randomization, Y_{*0} ; a fixed pre-index outcome status where appropriate, Y_{01} ; and a random clinic intercept, V_j , such as:

$$\text{logit}(BP<130/80 18m_{ji}) = Y_{00} + Y_{10}\text{CKD-CDS}_j + Y_{*0}\text{balancing}_j + Y_{01}\text{SBP index}_i + [V_j].$$

Parameter Y_{10} is expected to be positive and statistically significant, indicating that patients in clinics randomly assigned to receive the CKD-CDS intervention are more likely to meet CKD recognition (H1), ACEI / ARB use (H2), BP control (H3), A1C control (H4) and nephrology referral (H5) thresholds in the 18 months post-index than patients in UC clinics, accounting for random variation across clinics and their own pre-index status on these outcomes.

The difference in predicted likelihoods of meeting each of the 5 outcomes through 18 months post-index will be estimated via planned contrasts and reported for ease of interpretation.

Secondary outcomes may be calculated using different thresholds (e.g., A1c<8) or treated as continuous variables (e.g., SBP in mm Hg) with adaptations made to the analysis models as necessary (e.g., identity link). Secondary analyses may include assessing (a) rates of treatment intensification among patients not at their BP or glucose goals, (b) variation in CKD treatment patterns across PCPs, (c) treatment effect heterogeneity, (d) intervention costs, (e) rate of occurrence and time to major CV events, and (e) rate of occurrence and time to hospital admissions or emergency department visits by eligible study subjects by treatment arm. We may also assess the impact of the CKD-CDS on NSAID use and medication adherence and treatment heterogeneity across demographic and racial groups.

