9.4.2.2. Key Covariates. A key covariate in the H1-H5 hypothesis tests will be a binary indicator to denote whether the clinic in which the patient is seen was randomly assigned to the CKD-CDS intervention or the UC arm of the study. A second, pertinent to H3, quantifies the amount of time elapsed between the index visit and each measured BP. This covariate will be coded as (days since index/365) so that it quantifies the predicted annual change in BP control. Similarly, should the time elapsed between index and the last observed A1C differ by treatment group, log (time elapsed) may be included as an offset in the H4 analysis. Index CKD stage may be an important modifier of the CKD-CDS intervention. Stage 3-4 CKD will be defined based on the eGFR of 15-59 cc/min/1.73m² on the most recent eGFR test before the date of an index visit (stage 3a = 45-59, stage 3b = 30-44, stage 4 = 15-29), plus 1 or more antecedent eGFR values <60 cc/min/1.73m². Several other measures merit consideration as either secondary outcomes or as mediators or moderators of the primary analyses. These include (a) number of PCP patient encounters, (b) patient characteristics, including demographics and pre-intervention clinical

values and comorbidities (ICD-10 diagnosis codes and problem lists), and (c) PCP variation in baseline measures of CKD care.

9.4.2.3. Missing data. Data elements required for calculating the primary outcomes are extracted from EHR production tables. The absence of documentation of a care process, vital sign, or medication should not be interpreted as a missing value but rather as indicative of a care process or test not having been performed or medication not prescribed within the health system. Truly missing observations (eg, systolic BP measured, value not available) will be extremely rare, undetectable and assumed to be missing at random (MAR). The estimation techniques used in random coefficient models readily accommodate structural variation across observations in the amount of data present (eg, patients per clinic) and lead to unbiased parameter estimates and accurate standard errors when data are MAR.

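### The optional log-time offset in the H4 glucose analysis fixes an unsupported coefficient and shifts the treatment effect exactly when test timing differs by arm

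*Combined protocol and SAP*

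**What the plan says.** Section 9.1 defines the H4 outcome as "most recent A1c<7% in 1 to 18 months post-index". Section 9.4.1 says of the five measures "Each will be defined as a single outcome", and Section 9.4.2.1 says "each binary post-index outcome (e.g., recognition in 18m) will be predicted via a link function", with a random clinic intercept. The worked example there, for BP, uses a logit; no link is named for H4.

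Section 9.4.2.2 then adds a conditional step. Its trigger is worded "should the time elapsed between index and the last observed A1C differ by treatment group", and no test or threshold for a difference is given. When the trigger is met, an optional adjustment is allowed: "log (time elapsed) may be included as an offset in the H4 analysis". The sentence before it treats time in H3 as an ordinary covariate with an estimated coefficient.

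Three other places matter. The glucose care gap in Section 5.1 requires "most recent A1c>=7 on or before index date", so every H4 patient starts above goal. Section 8.1 leaves the test schedule open, "with the timing of care delivery driven by clinician and patient judgment". In Step 4 of Section 6.1.1, providers in the intervention arm can "order the recommendations suggested by the CDS such as labs, medication, e-consults or referrals to nephrology".

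**The concern.** An offset suits an outcome that accumulates in proportion to exposure. A1c status at the last test does not: it can move either way between tests. Fixing the coefficient at 1 therefore imposes a strong time trend that the data are not allowed to contradict.

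The trigger makes this worse. If the arms have the same timing, the offset hardly touches the treatment estimate. If timing differs, the fixed coefficient passes the difference straight into the parameter being tested, and that is the only situation in which the plan permits it. Earlier last tests in the intervention arm would create an apparent benefit; later ones would hide a real benefit.

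Time to the last A1c is also measured after index, and the intervention may change it. With no criterion for a difference and no commitment to use the term, the choice could be made after seeing the data, for one of five primary outcomes.

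**Working it through.** **1. The plan's own figure.** Table 2 gives a detectable difference of 5.2-7.0 points for A1c below 7%. Section 9.2 uses Neff = N / [1 + (n − 1) × ICC]. With N = 3,191 and 30 clinics, n = 106.4, so Neff = 2,887 at ICC .001 and 1,554 at ICC .01. At 80% power and two-sided 5%, with 40-50% at goal, the detectable difference is about 5.2 and 7.0-7.1 points. The figure is reproduced. On the log odds scale it is about 0.21 to 0.29. The plan gives no figure for the offset.

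**2. Algebra.** With the offset, logit(p) = a + b × treatment + 1 × log(t). Let D be the arm difference in mean log(t), intervention minus control.
- If the outcome does not depend on t, the estimate of b moves by about −D (exactly, if t is constant within arm).
- If the true coefficient of log(t) is g, the error in b is about (g − 1) × D with the offset and g × D without it.

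**3. Sample size for H4.** Only patients with A1c of 7% or more enter. Table 2 gives 3,191 × (1 − .487) = 1,637. Table 1 gives 2,066 × (1 − .503) × 30/17 = 1,812. These were simulated as 32 × 51 = 1,632 and 32 × 57 = 1,824, with 32 × 31 = 992 as an assumed low case.

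**4. Closed form.** At N = 1,632, 35% at goal (assumed) and ICC .003, the design effect is 1 + 50 × .003 = 1.15.

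SE = √[1.15 × 4 / (1,632 × .35 × .65)] = 0.111

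The false rejection rate is P(|Z + gap/SE| > 2.04), where 2.04 is the t cut-off on 30 df.

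**5. Simulation.** 1,000 trials per scenario, random-intercept logistic model, Wald test against t(30). Time was log-normal with log-SD .35 (assumed), clipped to 1-18 months, and the outcome did not depend on time. In the power column the intervention arm is tested later and the true rates are 35% and 45%.

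| Gap in mean log time | Medians (months) | False rejection, closed form | False rejection, simulated | Mean shift, intervention earlier | Power, intervention later |
|---|---|---|---|---|---|
| 0 | equal | – | 4% | – | – |
| 0.05 | 14 v 13.1 | 6% | 5-8% | +.049 | – |
| 0.10 | 14 v 12.4 | 13% | 12-14% | +.097 (OR 1.10) | 82% |
| 0.15 | 14 v 11.7 | 24% | 23-25% | +.147 (OR 1.16) | 67% |
| 0.20 | 14 v 11.1 | 40% | 38-40% | +.200 (OR 1.22) | 53% |

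Without the offset, false rejection is 3-5% and power is 96%. With log(t) as a covariate with an estimated coefficient, false rejection is 3-5% and the null treatment estimate stays within 0.006 of zero.

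**6. Sensitivity, at gaps 0.10, 0.15 and 0.20.**
- N = 992: 9%, 15%, 25%.
- N = 1,824: 13%, 27%, 41%.
- Control rate 25-45%: 12-13%, 23-25%, 34-42%.
- Complementary log-log link (600 trials, no simulated clinic effect, SE inflated for the design effect): 14%, 33%, 49%. Another link does not rescue the offset.
- Odds that truly rise with time, g = 0.25: about 20% at gap 0.20.

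**7. How easily the option opens.** Ignoring clustering, the SE of the gap is .35 × 2/√1,632 = .017. A gap of 1.96 × .017 = .034, or about 3.5% in time, would be nominally significant.

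**The case against.** The strongest reply is that the model in Section 9.4.2.1 already has no offset and that Section 9.4.2.2 only permits one. The link word before the H4 clause suggests the authors may have meant a covariate, as in H3. On that reading a one-word correction would do. But the text says offset, and an analyst following it would fit one.

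Several points stand as limits on size:
- The documents give no timing by arm, so the rejection rates are conditional on an assumed gap and on the option being used; they are not the plan's overall error rate.
- Chance alone would rarely give a gap above about .035. Usual care also has glycemic decision support (Section 6.1.1), so the larger gaps are not certain.
- The documents do not settle the direction. If the tool prompts more testing, last tests would tend to be later in the intervention arm, and the harm would be lost power rather than a false benefit.
- The inflation figures assume no effect of time. All patients start above goal, so the chance of being at goal may rise with time. At g = 0.5 the models with and without the offset are equally biased, in opposite directions.

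None of this supports a coefficient of exactly 1. The last point argues for estimating the coefficient as a check.

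**Conclusion.** The concern holds and should be fixed. The offset is wrong for H4 as defined, and its trigger selects the case in which it matters. The shift of about minus the gap is firm: simulated shifts were close to the full gap under no effect and 0.7-0.9 of it under a true effect.

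The consequence depends on the gap. At 0.05 it is small. At 0.10 false rejection is roughly two to three times nominal, and at 0.20 about eight times. These figures rest on a logit link, about 1,600 patients, 35% at goal, log-SD .35 and no true time effect. One of five primary outcomes is affected, and only if the option is used.

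**What to change.** Delete the offset sentence from Section 9.4.2.2. State that the primary H4 model has no time term and adjusts for index A1c and the randomization balancing factors. Report time to last A1c by arm in every case. Prespecify two sensitivity analyses:

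1. log(time) as a covariate with an estimated coefficient. It belongs here rather than in the primary model, because it is a post-index variable.
2. The last A1c in a common late window, for example 12-18 months, with the number of patients lacking one reported by arm. For the earliest index visits (April 2019) this window opens in April 2020, during the suspension of the tool described in Section 4.2, so it selects on testing and should be read with that in mind.

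A separate, minor point: the H3 time covariate does not share this defect, but its reference to every BP reading should be reconciled with the single averaged outcome in Section 9.1. As a post-index variable it also fits a sensitivity analysis better.

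The cost is SAP wording only: no new data and a simpler primary model.

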9.4.3 ANALYSIS OF THE SECONDARY ENDPOINT(S)

Not applicable

9.4.4 SAFETY ANALYSES

Trends in safety concerns for subjects will also be followed as indicated by the Data Safety and Monitoring plan outlined in the safety oversight section below.

9.4.5 BASELINE DESCRIPTIVE STATISTICS

Patient Characteristics. For each study subject, we document the following from EHR and/or health plan data sources: demographics (e.g., age, gender, race, ethnicity, insurance type, primary language, use of interpreter), vital signs (e.g., all BP values), height, weight, body mass index (kg/m²), laboratory values (including all serum creatinine, eGFR, electrolyte, and other renal function-related tests), medications prescribed (based on EHR prescribing data), and medication prescriptions filled (based on claims data). We calculate the ACC/AHA 10-year CVD risk score at defined time points (pre-index visit, at index visit, at follow-up visits).⁸⁰ Adjustment for patient covariates may be necessary because randomization is done at the clinic level, and patient-level data may therefore exhibit random as well as selection-induced covariate imbalance. Because they are drawn from EHR and/or health plan records rather than patient surveys, these data elements will be of high quality and available for virtually all subjects.

Provider Characteristics. We will have complete data for a limited set of provider characteristics, including age, years since graduation, gender, full-time versus part-time work status, physician versus allied provider (eg, nurse practitioner), specialty board certification status, employment years, and number and proportion of patients with CKD by CKD stage. Provider characteristics may be considered covariates or moderators to estimate the differential strength of the intervention across different kinds of providers.

9.4.6 PLANNED INTERIM ANALYSES

Not Applicable

9.4.7 SUB-GROUP ANALYSES

Several measures merit consideration as mediators or moderators of the primary analyses. These include (a) number of PCP patient encounters, (b) patient characteristics, including demographics and pre-intervention clinical values and comorbidities (ICD-10 diagnosis codes and problem lists), and (c) PCP

variation in CKD care at baseline. Assessment of heterogeneity of treatment effects based on pre-specified subgroups of patients will incorporate a factor (e.g. sex) and its interaction with treatment arm in mixed models.

9.4.8 TABULATION OF INDIVIDUAL PARTICIPANT DATA

Individual participant data will not be listed by measure and time point.

9.4.9 EXPLORATORY ANALYSES

We may examine the clinical impact of the CKD-CDS on the following: (1) non-aspirin NSAID use, (2) medication adherence, (3) provider behaviors such as treatment intensification among patients not at their BP or glucose goals, and CKD treatment patterns across primary care physicians (PCPs) (5) Rates of hypotension, hypoglycemia, electrolyte disturbances, emergency department visits, hospital admissions for renal and non-renal causes, major cardiovascular events, and mortality as deemed necessary per the data safety and monitoring plan.

10 SUPPORTING DOCUMENTATION AND OPERATIONAL CONSIDERATIONS

10.1 REGULATORY, ETHICAL, AND STUDY OVERSIGHT CONSIDERATIONS

10.1.1 INFORMED CONSENT PROCESS

10.1.1.1 CONSENT/ASSENT AND OTHER INFORMATIONAL DOCUMENTS PROVIDED TO PARTICIPANTS

A waiver of patient consent was requested and granted by the IRB for the following reasons:

a) All CKD-related treatment recommendations included in the CKD-CDS algorithms are evidence-based, as specified in national evidence-based clinical guidelines, and no care is advocated that is not evidence-based. Thus, the care recommendations conform to current standard of care and ought not represent any additional risk to patients beyond the routine risk that all patients assume whenever they have contact with the medical care system.

(b) The intervention identifies any current treatments that are potentially unsafe to the patient, which is of minimal risk to possible benefit to each patient at each visit during the study period.

(c) At intervention clinic training sessions and on every printed decision support screen and printed sheet, we emphasize that it is inappropriate for a PCP to implement suggested treatment recommendations without further checking the clinical status of a given patient.

(d) It would be impractical to consent patients (due to large numbers of patients and the intensity of clinic workflow) and impossible to answer the primary research questions (due to selection effects related to consent) if written informed consent of patients were required.

We are also received a waiver of informed consent for PCPs using the CKD-CDS tool for reasons (a), (b) and (c) above as well as the following reason(s): (d) the CDS tool, upon which the expansion to include CKD-CDS will be done for this study, is currently being used as part of standard care at HP and PN.

Consent will be obtained from providers who agree to be interviewed as part of the evaluation of the CDS tools, and the consent form and consenting process was reviewed and approved by the IRB.

In addition to the internal HealthPartners Institute policies, Health Insurance Portability and Accountability Act (HIPAA) itself makes specific provision for waiver of authorization to use PHI for research recruitment purposes under some specific conditions, all of which this study meets⁸¹.

At HealthPartners Medical Group, patients can opt out of use of their data for research. HealthPartners Institute keeps a record of the small number of individuals who have opted out to avoid use of their data or attempts to recruit them into studies. We will exclude patients who have declined permission for their medical records to be used in research.

10.1.1.2 CONSENT PROCEDURES AND DOCUMENTATION

Not-applicable.

10.1.2 STUDY DISCONTINUATION AND CLOSURE

This study may be temporarily suspended or prematurely terminated if there is sufficient reasonable cause. Written notification, documenting the reason for study suspension or termination, will be provided by the suspending or terminating party to participating clinics, investigators, study team members and the funding agency. If the study is prematurely terminated or suspended, the Principal Investigator (PI) will promptly inform participating clinics, the Institutional Review Board (IRB), and sponsor and will provide the reason(s) for the termination or suspension.

Circumstances that may warrant termination or suspension include, but are not limited to:

- Determination of unexpected, significant, or unacceptable risk to participants
- Demonstration of efficacy that would warrant stopping
- Insufficient compliance to protocol requirements
- Data that are not sufficiently complete and/or evaluable
- Determination that the primary endpoint has been met
- Determination of futility

Study may resume once concerns about safety, protocol compliance, and data quality are addressed, and satisfy the sponsor and IRB.

